2.4.5.7 Analyses of physical examination variables

Percentage of patients in each category of physical examination findings will be summarized by visit, site/system, and patient/dose group. Shift from baseline to worst and last postbaseline findings will also be summarized by site/system and patient/dose group.

2.4.6 Analyses of pharmacokinetic variables

All the pharmacokinetic parameters described in [Section 2.1.5](#) will be analyzed using the pharmacokinetic population.

Individual assessments and descriptive statistics (mean, standard deviation [SD], median, minimum, maximum, geometric mean, and percent coefficient of variation [CV%]) will be presented for plasma concentration time data and PK parameters for each dose level and visit. Individual and mean (SD) plasma concentration time profile will be presented graphically for each visit.

To evaluate the effect of immunogenicity on the PK of avalglucosidase alfa, the following plots will be presented:

- Individual profiles of avalglucosidase alfa concentrations over time at 6-month visit and yearly thereafter, grouped by patient/dose group and ADA status (ever positive, always negative, baseline ADA positive [preexisting ADA], neutralizing antibody positive)
- Median (SD) trough avalglucosidase alfa concentrations over time at 6-month visit and yearly thereafter, grouped by patient/dose group and ADA status (ever positive, always negative, baseline ADA positive [preexisting ADA], neutralizing antibody positive)

If relationships are apparent, further quantitative/statistical analysis may be performed (eg, statistical significance, correlation coefficients).

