a p value <0.05, TK parameter significantly different (40 vs 120 mg/kg fourth infusion).

b p value <0.01, TK parameter significantly different (40 vs 120 mg/kg fourth infusion).

c p value <0.001, TK parameter significantly different (40 vs 120 mg/kg fourth infusion).

d p value <0.05, TK parameter significantly different (120 mg/kg first vs fourth infusion).

e p value <0.01, TK parameter significantly different (120 mg/kg first vs fourth infusion).

Toxicokinetics were evaluated as part of the 6-month toxicology study in non-human primates. Avalglucosidase alfa TK parameters were evaluated following the 1st, 7th, and 13th infusion at the 50 and 200 mg/kg dose levels.

Across all infusions and both doses analyzed, avalglucosidase alfa elimination was biphasic. Toxicokinetics parameters were calculated only from the first phase of elimination, as the second phase had limited data points for analysis and represented GAA activity at, or very close to, background levels observed in vehicle-treated animals.

At infusion 1, 7, and 13 of avalglucosidase alfa, saturation kinetics were present (Table 3). These dose-related TK differences reached statistical significance with all 3 infusions analyzed. This strongly suggests that saturation kinetics is occurring between 50 and 200 mg/kg with avalglucosidase alfa in monkeys.

Intradose TK parameters appeared to change with successive infusions (ie, infusion 1, 7, and 13). These changes were characterized by increases in C_{max}, t_{1/2}, and AUC, and decreases in CL. Compared to the first infusion of 50 mg/kg, most TK parameters were significantly different for both the 7th and 13th infusions. At 200 mg/kg, compared to the first infusion, most TK parameters exhibited a trend for differences at infusion 7 and significant differences at infusion 13. Toxicokinetic parameter changes observed between infusion 1, 7, and 13 suggest that repeated dosing in the monkey at the dose levels tested affects the TK profile of avalglucosidase alfa.

For both dose levels and infusions, avalglucosidase alfa TK did not appear to differ between male and female monkeys.

Table 3 - Toxicokinetic parameters for avalglucosidase alfa following the 1st, 7th, and 13th intravenous infusion to cynomolgus monkeys at a dose of 50 and 200 mg/kg

Parameter	50 mg/kg			200 mg/kg		
	1st Infusion (n=12)	7th Infusion (n=11)	13th Infusion (n=10)	1st Infusion (n=12)	7th Infusion (n=11)	13th Infusion (n=8)

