8 STUDY TREATMENTS

8.1 INVESTIGATIONAL MEDICINAL PRODUCTS

Avalglucosidase alfa, the investigational medicinal product (IMP), will be supplied as a sterile, nonpyrogenic, lyophilized product in single-use 20 mL vials containing approximately 100 mg of avalglucosidase alfa in 10 mM histidine, 2% glycine, 2% mannitol, and 0.01% polysorbate 80, with a pH of 6.2.

Avalglucosidase alfa will be administered by IV infusion following reconstitution and dilution at a dose of 20 mg/kg body weight qow.

The total amount of investigational product administered may be adjusted as needed to account for changes in body weight. Most recent body weight should be used for dose calculation. Each avalglucosidase alfa IV infusion will be administered in a step-wise manner. The rate will begin at a slow initial rate and will be gradually increased if there are no signs of IARs, until a maximum rate is reached. The infusion length will be dependent on the dose. Specific details pertaining to the infusion volumes and rates as well as dose calculation can be found in the pharmacy manual.

Prior to each infusion, the patient should be assessed by the Investigator or appropriate designee (ie, qualified physician with the exception of patients who receive home infusion of avalglucosidase alfa as outlined below under the subsection “Home infusion”) to determine if the patient is free of acute illness and is clinically stable to receive the infusion. Infusions will be postponed (see [Section 8.7.1](#)) if the patient is acutely ill on the scheduled day of infusion. Any modification to the dose and/or frequency of dosing is not permitted unless it is due to an AE, in which case it is not a protocol violation, but the Investigator must consult with the Sponsor in the event of a dose change. No dose increase above the maximum recommended dose of 20 mg/kg qow will be allowed for any patients.

Patients will be required to remain in the hospital or the infusion center for observation of AEs for 1 hour after each infusion; see below for the patients receiving home infusion. Patients may be required to stay for a longer observation period at the Investigator’s discretion. In case the patient does not stay for this observation period (eg, as part of contingency measures for a regional or national emergency that is declared by a governmental agency), the Investigator (or appropriate designee) will contact the patient to ensure that no adverse event occurred during the observational period.

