8.7.1 Treatment accountability and compliance

Administration of the IMP is performed in collaboration with qualified study personnel, and under the responsibility of the Investigator or the subinvestigator.

- IMP accountability:
 - The person responsible for drug dispensing is required to maintain adequate records of the IMP. These records include the date and number of treatment units received from the Sponsor, dispensed for patient, and destroyed or returned to the Sponsor,
 - The person responsible for drug administration to the patient will record precisely the date, time of the drug administration, and number of treatment units used for administration,
 - The Investigator records the dosing information on the appropriate page(s) of the eCRF,
 - The monitor in charge of the study then checks the eCRF data by comparing them with the IMP which he/she has retrieved and IMP records.

The patient's compliance with the treatment regimen will be monitored in terms of the patient receiving the study drug infusion every other week within a ± 7 -day window from the previous infusion date. Missed, delayed, or incomplete infusions will be clearly documented and considered in the analysis. Missed doses of study treatment due to sickness, safety concerns, or for medical reasons are not protocol deviations, but must be documented for analysis and potential impact on the study results.

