9.2 PHARMACOKINETICS

9.2.1 Sampling times

Blood samples for evaluation of avalglucosidase alfa PK will be collected before, during, and after avalglucosidase alfa infusions at 6 months and then yearly thereafter for the first 6 years.

Sampling times are as follows: pre-dose (prior to infusion), at the end of the infusion, and at 1, 4, 8, 12, and 24 hours after infusion. The following PK blood samples are to be collected within 15 minutes of scheduled time: pre-dose and all samples immediately following the end of the infusion through 8 hours post infusion. Pharmacokinetic samples collected 12 hours through 24 hours post infusion are to be collected ± 2 hours of the scheduled time.

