9.2.4 Bioanalytical methods

Plasma samples will be analyzed using validated, sensitive and specific bioanalytical methods, namely, a fluorometric assay using a 4-methylumbelliferyl- α -D-glucoside (4-MUG) substrate to detect avalglucosidase alfa activity.

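### The trough plot in SAP 2.4.6 cannot show a loss, or moderate gain, of exposure due to ADA, yet it is that section's only group-level summary by ADA status

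*SAP*

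**What the plan says.** SAP 2.4.6 names two plots for the effect of immunogenicity on PK:

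1. "Individual profiles of avalglucosidase alfa concentrations over time at 6-month visit and yearly thereafter, grouped by patient/dose group and ADA status"
2. "Median (SD) trough avalglucosidase alfa concentrations over time at 6-month visit and yearly thereafter, grouped by patient/dose group and ADA status"

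It then adds: "If relationships are apparent, further quantitative/statistical analysis may be performed (eg, statistical significance, correlation coefficients".

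The SAP does not define trough. Protocol 9.2.1 sets the PK samples at "pre-dose (prior to infusion), at the end of the infusion, and at 1, 4, 8, 12, and 24 hours after infusion". Protocol 8.1 gives the drug "at a dose of 20 mg/kg body weight qow", and protocol 8.7.1 monitors compliance as "receiving the study drug infusion every other week within a" window of plus or minus 7 days. Protocol 9.2.4 describes a fluorometric assay with a "substrate to detect avalglucosidase alfa activity".

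Two other places deal with ADA and PK. Protocol 11.6.2 plots pre-dose ADA and neutralizing titers against clearance at 6 months and yearly. SAP 2.4.5.6 lists three AUC outputs: within-subject change by peak titer category, a comparison of ADA-positive with ADA-negative patients using the titer category at the PK assessment, and a table of AUC and percent change from Day 1 by peak titer category. It introduces them as options for switched patients. SAP 2.4.6 has no clearance plot, and the list of modifications in SAP 1.6 does not mention dropping one.

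**The concern.** A trough is a useful exposure measure when a readable amount of drug is left at the end of the dosing interval. Here the interval is two weeks and the documented plasma half-lives are minutes to 2 hours. The assay measures enzyme activity. For the 6-month monkey study, protocol 4.1.2 says that the second elimination phase "represented GAA activity at, or very close to, background levels observed in vehicle-treated animals". The trough panel is therefore likely to show assay background, split by ADA status.

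PK is part of the primary objective. If ADA halved or doubled exposure, the trough curves would look the same as with no effect. The panel is also one of the two displays on which the decision about further quantitative analysis depends, and it is the only one in the section that summarises groups rather than individuals.

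**Working it through.** **Inputs.** Dosing interval: 14 days = 336 h (protocol 8.1). With the 7-day window it is 168 to 504 h (protocol 8.7.1). Half-lives (protocol 4.1.2): 26.9 min in GAA knockout mice; 0.315 to 0.939 h in CD-1 mice (Table 1); 0.508 to 0.919 h (Table 2) and 0.525 to 1.99 h (Table 3) in monkeys. The monkey values come from the first elimination phase only. Highest mean Cmax: 5284 µg/mL (Table 3, 200 mg/kg, 13th infusion).

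**Reproducing the longest half-life.** With the definitions in protocol Table 4, t½ = 0.693 × Vz / CL. For the 13th infusion at 200 mg/kg: 0.693 × 22.2 / 7.88 = 1.95 h, against 1.99 h stated (−1.9%). The other columns of Tables 1 to 3 agree within 7%, as expected when ratios are taken of group means.

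**Fraction left at the trough.** Fraction = 2^(−T / t½), ignoring the infusion length, which the documents do not give.

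- t½ = 1.99 h, T = 336 h: 336 / 1.99 = 169 half-lives. From 5284 µg/mL this leaves about 8e-48 µg/mL. With the half-life doubled to 3.98 h it leaves about 2e-22 µg/mL. These figures extrapolate one phase and mean only that the value is zero to any assay.
- t½ = 1.99 h, T = 168 h: 84 half-lives, fraction about 4e-26.
- Human half-life, assumed 0.5 to 10 h, T = 336 h: 672 to 33.6 half-lives. At 10 h the fraction is 2^(−33.6), about 8e-11.
- For a trough of 0.1% of the end-of-infusion level at 336 h: t½ = 336 / log2(1000) = 33.7 h.

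**What the other samples can show.** Assume a 2 h half-life and fixed volume. Doubled clearance then gives 1 h, and halved clearance gives 4 h. Fraction of the end-of-infusion level:

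| Time after infusion | CL doubled (1 h) | Unchanged (2 h) | CL halved (4 h) |
|---|---|---|---|
| 4 h | 0.0625 | 0.25 | 0.5 |
| 8 h | 0.0039 | 0.0625 | 0.25 |
| 12 h | 0.00024 | 0.0156 | 0.125 |
| 336 h (trough) | 7e-102 | 3e-51 | 5e-26 |

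AUC is halved, unchanged or doubled across the three columns. The post-infusion samples separate the cases; the trough does not.

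**When a trough could be seen.** No quantification limit is given. Assuming Cmax of 200 to 5284 µg/mL and a limit of 0.001 to 1 µg/mL, the half-life needed is T / log2(Cmax / limit). At 336 h this is 15 to 44 h, or 7.5 to 22 times a 2 h half-life. At 168 h it is 7.5 to 22 h, or 3.8 to 11 times.

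**The case against.** The main objection is about scope. A reader might infer that the whole ADA-by-PK evaluation is blind and would read as no effect whatever ADA does to exposure. The documents do not support that, for four reasons:

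- The first plot in SAP 2.4.6 shows individual profiles by the same ADA status, including the end-of-infusion and 1 to 24 h samples.
- SAP 2.4.5.6 lists AUC outputs by titer that do not depend on a relationship looking apparent. The condition in SAP 2.4.6 follows both plots, so the profiles alone could trigger further work.
- Nothing in either document says that flat troughs would be reported as absence of an effect.
- A very large prolongation of half-life, roughly 7.5-fold or more at day 14 under the assumptions above, could show.

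These points stand and limit the finding to the trough plot.

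The half-lives are also animal values, and the later phase in monkeys had too few data to fit. This stands as a caveat. It does not rescue the plot, because the conclusion at 336 h holds at 10 h, five times the longest documented value. At the shortest interval it is less absolute: with 168 h and a 10 h half-life, 2^(−16.8) or about 9e-6 remains, which a sensitive assay might detect. The long tissue half-life mentioned in protocol 4.2.2.1 concerns tissue and the length of adverse event follow-up, not plasma.

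Fixed-time concentrations are not a perfect substitute. At a 0.5 h half-life, the 8 h sample holds only 1.5e-5 of the end-of-infusion level. This stands, and it is why clearance and AUC should lead.

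**Conclusion.** The point holds for the trough plot. At the planned two-week interval it cannot show any loss, or a moderate gain, of exposure due to ADA. This rests on two assumptions: that trough means the pre-dose sample, the only scheduled one that fits, and that the human plasma half-life does not exceed about 10 h. The documents give neither a human half-life nor a quantification limit.

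The consequence is limited but real. SAP 2.4.6 is left with no informative group-level display by ADA status. Because of how the AUC outputs in SAP 2.4.5.6 are introduced, treatment-naive patients have only the individual profiles clearly specified, and the clearance display in protocol 11.6.2 has no counterpart in SAP 2.4.6. The analysis is descriptive and no decision rule depends on it. The change is worth making because it is nearly free.

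**What to change.** In SAP 2.4.6:

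- Replace the trough bullet with clearance and AUC, by patient/dose group and by ADA status or titer at that PK visit, for all patients. This restores agreement with protocol 11.6.2. End-of-infusion and early post-infusion concentrations can be added. Dose normalisation is not needed: the plots are already grouped by dose, and the kinetics are saturable (mouse AUC/dose is 12.5 at 4 mg/kg and 37.4 at 40 mg/kg, protocol Table 1).
- Keep pre-dose values in the listings as a check of assay background.
- Drop the condition that a relationship must first look apparent. Where numbers permit, report at each PK visit the ADA-positive to ADA-negative geometric mean ratio, or the rank correlation with titer, with a 95% CI, labelled descriptive.

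In SAP 2.4.5.6, state firmly which patients the AUC outputs cover.

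The cost is SAP wording and one replaced figure. The samples are already in the seven-point profile. The downside is wide intervals in a study that the SAP itself describes as small.

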2.4.7 Analyses of pharmacodynamic variables

Pharmacodynamic variables are described in [Section 2.1.6](#).

Descriptive statistics (including mean, SD, median, minimum, maximum, and 95% confidence intervals (CI) of changes) for both observed and change from baseline (and/or rebaseline, if specified) by study visit will be provided for quantitative parameters, by group and by each patient group/dose level, unless otherwise specified. Qualitative results that are categorical will be presented with number and percentage of patients in each category. If a linear trend in the change of a pharmacodynamic endpoint is observed, a longitudinal model may be employed to model change from baseline over time.

Muscle MRI

MRI data collected from the TDR12857 and LTS13769 studies will be summarized separately, due to the updated methods used for LTS13769. The Week 27 results from TDR12857 will be used as the LTS13769 baseline for LTS13769 study (see [Section 2.5.1](#)). Descriptive statistics will be used for quantitative parameters to summarize changes over time from baseline/rebaseline for each study. The Mercuri grading will be presented both as a categorical variable (ie, number and percentage of patients in each grade over time will be presented) and as a continuous variable (ie, number, mean, SD, median, minimum, maximum, and 95% CI will be presented at each visit). Additional summaries will be presented for the patients previously allocated to the 5 or 10 mg/kg dose groups in the TDR13857 study and switched to 20 mg/kg in the LTS13769 study (see [Section 2.5.1](#)). The number of patients with abnormally high values for any specific muscle, as indicated by a T2 of >39 ms, will be presented using descriptive statistics.

Muscle biopsy

Changes from the TDR12857 baseline over time will be used to summarize continuous variables. For qualitative measures, number and patients in each category over time will be presented.

A correlative measure comparing the biopsied muscle and its MRI counterpart will also be performed.

Urine Hex4

Urine Hex4 levels will be summarized using descriptive statistics at each scheduled study visit. Observed measurements, as well as change from baseline, will be summarized. If a linear trend in the change of urine Hex4 levels is observed, a longitudinal model may be employed to model change from baseline over time. In addition, 95% CIs of changes will be presented. Due to the small number of patients, nonlinear relationship will not be formally characterized.

PK and urine Hex4

To explore the relationship between PK endpoints and urine Hex4 levels, correlational statistics (Spearman or Pearson) at select visits where PK and urine Hex4 are assessed will be used. In addition, scatter plots and linear regression analysis may be used to describe the relationship between PK endpoints and urine Hex4 levels as appropriate.

2.4.8 Pharmacogenetics

Analyses of serum skeletal muscle RNA expression analysis and plasma circulating microRNA levels will be reported in a separate report.

2.4.9 Analyses of quality of life/health economics variables

Not applicable.

2.5 DATA HANDLING CONVENTIONS

2.5.1 General conventions

Baseline is defined as the last observation prior to the first treatment in the TDR12857 study, unless otherwise specified. In addition, a rebaseline value may be used for the summaries of select assessments for patients who previously enrolled in the 5 and 10 mg/kg dose groups and switched to the 20 mg/kg dose in the LTS13769 study, in order to compare changes before and after the switch. (In some cases, assessments were not repeated at the rebaseline visit, depending on the last available assessment dates [see protocol Section 10.1.2.7]. In such circumstances, the last available assessments prior to dose switch will be used for the rebaseline values of the parameters of interest.)

Due to the centralized MRI reading procedures, there will be multiple Week 27 values, as the Week 27 image will be reread in accompany to each LTS13769 MRI read. The LTS13769 baseline will be the mean of the multiple Week 27 of the particular parameter. The previous Week 27 reads performed during the TDR12857 study will be presented in the presentation of data collected during the TDR12857 study period, but excluded in the calculation of the LTS13769 baseline, as the vendor [same vendor used for TDR12857] has upgraded their image processing capabilities.

2.5.2 Data handling conventions for secondary efficacy variables

None.

2.5.3 Missing data

No imputation (single or multiple) is planned for this study.

For categorical variables, patients with missing data are not included in calculations of percentages unless otherwise specified. When relevant, the number and percentage of patients with missing data is presented.

Handling of computation of treatment duration if investigational medicinal product end of treatment date is missing

For the calculation of the treatment duration, the date of the last dose of IMP is equal to the date of last administration reported on the end-of-treatment CRF page. If this date is missing, the exposure duration should be left as missing.

The last dose intake should be clearly identified in the CRF and should not be approximated by the last returned package date.

Handling of medication missing/partial dates

No imputation of medication start/end dates or times will be performed. If a medication date or time is missing or partially missing and it cannot be determined whether it was taken prior or concomitantly, it will be considered a prior, concomitant, and posttreatment medication.

Handling of adverse events with missing or partial date/time of onset

Missing or partial adverse event onset dates and times will be imputed so that if the partial adverse event onset date/time information does not indicate that the adverse event started prior to treatment or after the treatment-emergent adverse event period, the adverse event will be classified as treatment-emergent. No imputation of adverse event end dates/times will be performed. These data imputations are for categorization purpose only and will not be used in listings. No imputation is planned for date/time of adverse event resolution.

Handling of adverse events when date and time of first investigational medicinal product administration is missing

When the date and time of the first IMP administration is missing, all adverse events that occurred on or after the day of randomization should be considered as treatment-emergent adverse events. The exposure duration should be kept as missing.

The last dose intake should be clearly identified in the CRF and should not be approximated by the last returned package date.

Handling of missing assessment of relationship of adverse events to investigational medicinal product

If the assessment of the relationship to IMP is missing, then the relationship to IMP has to be assumed and the adverse event considered as such in the frequency tables of possibly related adverse events, but no imputation should be done at the data level.

Handling of missing severity of adverse events

If the severity is missing for 1 of the treatment-emergent occurrences of an adverse event, the maximal severity on the remaining occurrences will be considered. If the severity is missing for all the occurrences, a “missing” category will be added in the summary table.

Handling of potentially clinically significant abnormalities

If a patient has a missing baseline he will be grouped in the category “normal/missing at baseline.”

For PCSAs with 2 conditions, one based on a change from baseline value or a normal range and the other on a threshold value, with the first condition being missing, the PCSA will be based only on the second condition.

For a PCSA defined on a threshold and/or a normal range, this PCSA will be derived using this threshold if the normal range is missing; eg, for eosinophils the PCSA is > 0.5 GIGA/L or $> \text{ULN}$ if $\text{ULN} \geq 0.5$ GIGA/L. When ULN is missing, the value 0.5 should be used.

Measurements flagged as invalid by the laboratory will not be summarized or taken into account in the computation of PCSA values.

Handling of Repeat Laboratory measurements on the same day

The average values will be used for the repeat laboratory measurements taken on the same day for each visit.

Handling of ADA titer with missing or non-numerical values

If the ADA titer is reported as “<value”, then the actual value is imputed as this value. For example, “<100” will be imputed as 100. A negative ADA status will be assumed as a value of 0 (will be excluded when geometric mean of the group needs to be calculated).

